7.5.5 Pregnancies

A listing of pregnancy test results will be provided.

7.6 Analysis of PK

The statistical methods for PK data will be described in a separate analysis plan. Results of the population PK analysis will not be reported in the Clinical Study Report but in a separate population PK report.

Plasma concentration data of roxadustat will be listed.

7.7 Analysis of PD

Not Applicable.

7.8 Subgroups of Interest

Selected efficacy and safety endpoints will be summarized for the subgroups defined on the basis of the categorized variables listed below in Table 25

Table 25 Subgroups of interest

Grouping variables	Subgroups
Age group	< 65 years 65 - 74 years ≥ 75 years
Sex	Female Male
Region	Western Europe Rest of the World
Baseline Hb	≤ 8 g/dL > 8 g/dL
History of cardiovascular, cerebrovascular or thromboembolic diseases	Yes No
Table continued on next page	

Grouping variables	Subgroups
Baseline eGFR	< 30 mL/min/1.73m ² ≥ 30 mL/min/1.73m ²
Baseline eGFR ¹	< 15 mL/min/1.73m ² ≥ 15 mL/min/1.73m ²
Baseline CRP ²	≤ ULN > ULN
Baseline Iron Repletion Status ²	(TSAT ≥ 20% and ferritin ≥ 100 ng/mL) vs (TSAT < 20% or ferritin < 100 ng/mL)
¹ : only for the two primary efficacy endpoints and also for selected AE summaries.	
² : only for the two primary efficacy endpoints and the key secondary endpoint on Hb (week 28- week 36)	

7.9 Other Analyses

The current analysis plan is based on version 2.0 of the protocol. An exploratory analysis on Hb maintenance will be conducted in the sub-set of patients treated for at least 24 weeks under protocol version 1.0. The sub-set includes patients that discontinued treatment prior to Week 24 under protocol version 1.0. The pooled roxadustat arm will be separated into 3 groups according to their randomized treatment: (TIW, BIW, QW). Tables with summary statistics by visit up to Week 24 will be derived for the Hb values and the average weekly prescribed dose by the 4 treatment groups (placebo, roxadustat TIW, roxadustat BIW, roxadustat QW). In addition, the change from baseline to the Hb value average over Weeks 12-24 (excluding rescue medication) will be analysed using the MMRM model using Hb and eGFR at baseline as co-variates. In addition, average weekly dose will be summarized by treatment arm by 4-weekly period until subject switched to protocol version 2.0.

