12.3 Appendix 3: Instructions for Subjects Moving from Protocol v1.0 to Protocol v2.0

Visit Schedule

Subjects who have entered the study under protocol v1.0, upon signing the updated informed consent, adapted their visit frequency according to [Table 1](#) Schedule of Assessments. For example, if the subject signs the informed consent for protocol v2.0 at scheduled week 3 (according to protocol v1.0), subject will attend clinic at week 4, week 6 and all subsequent visits as per Schedule of Assessments.

Dosing Instructions for Subjects Moving from Protocol v1.0 to Protocol v2.0 Dosing

Study drug will be dosed TIW throughout the Treatment Period, unless otherwise specified.

Subjects who have entered the study under protocol version 1.0 should, upon signing the updated informed consent, adapt their dose frequency and dose amount. At this visit it is first determined if the subject would need a dose titration according to the dose adjustment rules as per Section [5.1.2](#). Once that is established, patients are converted per the below instructions. The dose assigned must not exceed the maximum allowed dose of 3.0 mg/kg bodyweight or 300 mg per administration, whichever is lower. For subjects on permanent dialysis dose assigned must not exceed 3.0 mg/kg (based on dry weight in HD subjects and weight minus abdominal fluid based on last filling in peritoneal dialysis subjects) or 400 mg per administration, whichever is lower.

- a) Subjects in the correction period or maintenance period on TIW dosing, will continue on TIW dosing for the remainder of the treatment period. If needed their dose will be adjusted according to the conversion table below, at the visit when the updated informed consent is signed.

Current TIW dose (mg)	20	40	50	70	100	120	150	200	250	300	350	400
If no dose titration needed	20	40	50	70	100	100	150	200	250	300	300	300
If up titration needed*	40	50	70	100	150	150	200	250	300	300	300	300
If down titration needed*	#	20	40	50	70	100	100	150	200	250	300	300

- b) Subjects in the maintenance period on BIW dosing will change to TIW dosing immediately, per the conversion table below, at the visit when the updated informed consent is signed.

Current BIW maintenance dose (mg)	20	40	50	70	100	120	150	200	250	300	350	400
If no dose titration needed	20	20	40	50	70	70	100	150	150	200	250	250
If up titration needed*	20	40	40	70	70	100	150	150	200	250	250	300
If down titration needed*	#	20	20	40	50	70	70	100	150	150	200	200

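### SAP 7.9's exploratory v1.0 dosing-frequency analysis, as written, admits subjects who stopped before Week 24 under v1.0 but has no entry route for subjects still on treatment who converted to v2.0 before Week 24

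*SAP*

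**What the plan says.** SAP 7.9 defines its population in two sentences. The first sets the core group: "An exploratory analysis on Hb maintenance will be conducted in the sub-set of patients treated for at least 24 weeks under protocol version 1.0". The second extends it: "The sub-set includes patients that discontinued treatment prior to Week 24 under protocol version 1.0". No limit on randomization date is attached to either sentence.

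In this set, Hb and average weekly prescribed dose are tabulated by visit up to Week 24 for placebo and roxadustat TIW, BIW and QW, and "the change from baseline to the Hb value average over Weeks 12-24 (excluding rescue medication) will be analysed using the MMRM model". A last sentence adds that "average weekly dose will be summarized by treatment arm by 4-weekly period until subject switched to protocol version 2.0". No matching rule on data up to the switch is given for Hb.

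Protocol Appendix 3 (12.3) explains how subjects leave v1.0: "Subjects who have entered the study under protocol version 1.0 should, upon signing the updated informed consent, adapt their dose frequency and dose amount". For maintenance dosing it states: "Subjects in the maintenance period on BIW dosing will change to TIW dosing immediately"; QW subjects are treated likewise. Its worked example for the visit schedule is a subject who re-consents at scheduled Week 3, so conversions well before Week 24 were expected.

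Elsewhere the SAP pools the v1.0 frequencies (3.3 and 6.5.4). Section 7.9 is the only planned analysis that separates them.

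**The concern.** Take a subject randomized 15 weeks before conversion. If that subject stops at Week 10, the second sentence of the definition lets them in. If the same subject is still on treatment at Week 15 and converts, they have neither 24 weeks under v1.0 nor a discontinuation under v1.0, and they are out. For everyone randomized less than 24 weeks before conversion, membership therefore depends on a post-randomization outcome.

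Two things follow. The set holds more stoppers than the v1.0 population produced. And Hb collected before conversion is thrown away, although some of it falls in the Weeks 12-24 window.

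The MMRM does not repair this. It handles missing visits for subjects who are in the model, whereas here whole subjects are removed beforehand. The groups are also small to begin with, because v1.0 randomized to six arms (SAP 3.2.3).

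**Working it through.** The plan states no figure for this analysis, so there is nothing to reproduce. The check asks how far the written rule changes the make-up of the set.

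**Inputs**
- Entry rule: SAP 7.9, as above.
- E, the weeks of v1.0 enrolment before conversion: not in the documents. Assumed 30 to 100, with uniform entry. For orientation, the protocol synopsis starts the planned study period in 1Q2013 and SAP section 1 dates v2.0 17 December 2014. That is 626 to 715 days, or about 89 to 102 weeks. The actual first randomization and the site conversion dates are not given.
- d, the probability of stopping by Week 24: not in the documents. Assumed 20%, constant hazard, with 10% and 30% for comparison.

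**Formulas.** Let λ = -ln(1 - d)/24. In units of one week's enrolment:
- Stoppers kept: S = (24 - d/λ) + (E - 24)d
- Subjects with 24 weeks under v1.0: C = (E - 24)(1 - d)
- On-treatment converters dropped: W = d/λ
- Stopper share of the set = S/(S + C); fraction dropped = W/E

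**At d = 0.20:** λ = 0.2231/24 = 0.009298, d/λ = 21.51, 24 - d/λ = 2.49.

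| E (weeks) | S | C | Stopper share | Dropped = 21.51/E |
|---|---|---|---|---|
| 30 | 2.49 + 1.2 = 3.69 | 4.8 | 43% | 72% |
| 40 | 2.49 + 3.2 = 5.69 | 12.8 | 31% | 54% |
| 52 | 2.49 + 5.6 = 8.09 | 22.4 | 27% | 41% |
| 78 | 2.49 + 10.8 = 13.29 | 43.2 | 24% | 28% |
| 100 | 2.49 + 15.2 = 17.69 | 60.8 | 23% | 22% |

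The share without selection would be 20%. At d = 10% it is 25%, 16% and 14% for E = 30, 40 and 52; at d = 30% it is 57%, 43% and 38%.

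**Usable data lost.** Converters with at least 12 weeks under v1.0: (√0.8 - 0.8)/λ = 0.0944/0.009298 = 10.16. Divided by 21.51, that is 47% of those dropped, whatever the value of E.

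**Effect on by-visit observed means.** Many stoppers leave too early to have Hb in Weeks 12-24. Allowing Hb up to 7 days after the last dose, 56% to 65% of included stoppers have none (d = 20%, E = 52 to 30). Over the scheduled visits from Week 12 to Week 24, stoppers supply 10.9%, 8.1% and 7.4% of observed values at E = 30, 40 and 52, against 6.4% without selection. If stoppers' Hb change is 1.0 g/dL lower (an assumption), the mean shifts by:
- E = 30: (0.109 - 0.064) × 1.0 = 0.045 g/dL
- E = 40: (0.081 - 0.064) × 1.0 = 0.017 g/dL
- E = 52: (0.074 - 0.064) × 1.0 = 0.010 g/dL

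**Effect on contrasts.** If every stopper counted in full, the shift in one arm would be (share - d) × 1.0 g/dL. For one arm stopping at 20% and another at 10%, the difference between those shifts is 0.235 - 0.152 = 0.08 at E = 30, 0.108 - 0.064 = 0.04 at E = 40, and 0.065 - 0.038 = 0.03 g/dL at E = 52. With equal stopping and an equal Hb gap in both arms it is zero.

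**The case against.** **The author may have meant something narrower.** The second sentence of the definition could be meant to keep stoppers only within the cohort that could have reached 24 weeks under v1.0, to avoid a completers-only analysis. On that reading the stopper share is not inflated. But the text sets no such limit, a programmer following it would not apply one, and converters' earlier Hb would still go unused.

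**The dose sentence does not rescue the Hb analyses.** Summarizing dose until the switch also makes sense for subjects who converted after Week 24, so it does not show that earlier converters are included.

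**Stronger readings that the documents do not support**
- A reader might infer that everyone who stopped before Week 24 is kept. Only those who stopped while still under v1.0 are; a subject who converted and then stopped is also outside the set.
- A reader might take the full-weight shift at 20% stopping and E = 30 to 52 (0.07 to 0.24 g/dL) as the error in the tables. SAP 7.11.1 does not impute endpoints without inferential analysis, so the observed-data figures above apply to the by-visit tables. The larger figure could be approached only in the MMRM mean, through implicit extrapolation for stoppers. At 78 to 100 weeks even the full-weight figure is only about 0.03 g/dL.
- A reader might infer that the frequency comparison is biased in any case. The rule is the same in every arm, and all three frequencies used TIW during correction (SAP Table 9). Contrasts are distorted only if stopping differs by arm, or relates to Hb differently by arm.

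**What stands:** the analysis is exploratory, carries no success criterion and lies outside the testing sequence in SAP 7.4.2. Requiring a period of possible v1.0 exposure is also reasonable for a maintenance question, provided that it is defined without reference to stopping.

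**Conclusion.** The concern holds for the definition as written. Its direction is certain if some subjects converted and some stopped before Week 24; its size is not known. It rests on the assumed entry pattern, enrolment length and stopping rate. If recruitment was still accelerating at conversion, more subjects fall within the last 24 weeks and the effect is larger for a given E. Under the assumptions shown, the over-representation is slight with a long v1.0 period and marked with a short one. The loss of usable subjects is substantial throughout, at about a fifth or more of v1.0 subjects. The consequence for observed Hb means is small and for the MMRM mean possibly larger. This is a low-priority correction: no primary or key secondary result depends on it.

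**What to change.** Amend SAP 7.9 in one of two ways.

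1. Define the set as all subjects randomized under v1.0. Use Hb up to the date of conversion to v2.0 or discontinuation, and set post-conversion visits to missing in the MMRM. This extends to Hb the cut at the switch that 7.9 already applies to its dose summary.
2. Restrict the set to subjects randomized at least 24 weeks before their site's v2.0 implementation date, whether or not they stopped. A site date is needed because a subject who stopped under v1.0 may have no conversion date.

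Either costs one sentence and a changed population flag, with no new data collection; the second also needs the site implementation dates. The first keeps more subjects. Its drawback is that some of them converted during the common TIW correction phase and carry little information on maintenance frequency. The second stays closer to the maintenance question but still leaves out later entrants' Hb. Under either option, report by arm how many subjects converted and how many stopped before Week 24.

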7.10 Interim Analysis (and Early Discontinuation of the Clinical Study)

The study will have no interim analysis with statistical inference. Safety data and dosing decisions will be monitored on an ongoing basis. Ongoing review of safety data will be completed by an independent Data and Safety Monitoring Board (DSMB).

7.11 Handling of Missing Data, Outliers, Visit Windows, and Other Information

7.11.1 Missing Data

For relevant analyses without rescue therapy, for subjects who used rescue therapy, the reported Hb values after the initiation of rescue therapy will be set to missing (instead of the reported values) for 6 weeks from the start date of rescue therapy (or the end in case the duration of rescue therapy > 1 day).

The following imputations will be performed for the continuous endpoints, unless specified otherwise :

- An MMRM model will be run for the purpose of implicit imputation of missing data by using all the available information from the observed data via the within-patient correlation structure for continuous endpoints with inferential analysis.

- An ANCOVA model with multiple imputations (MI) will also be run.

No imputations will be done for endpoints with no inferential analysis.

7.11.2 Missing Dates

As a general rule, the worst case scenario imputation rule is usually used. A start date is generally imputed to the first possible day, unless the available information in the partly missing date is equal to the one in the reference date. In this case, the substituted date is set to the reference date. An end date is generally imputed to the last possible day.

Completely missing dates will not be imputed.

Diagnosis of anemia, CKD and Targeted Medical History

The following rules will be applied to impute partially missing dates of diagnosis of Anemia, CKD and targeted medical history, as defined in [Table 26](#) below.

Table 26 Definitions of the Analysis Date of Diagnosis of Anemia, CKD and Targeted Medical History

Reported Date (from the eCRF)	Analysis Date (Derived)
--/MM/YYYY	01/MM/YYYY
--/--/YYYY	01/01/YYYY
DD/--/----, or --/MM/----, or --/--/----	No imputation

Previous or Concomitant medication:

For previous or concomitant medications, including rescue medications and chronic dialysis, partially missing start dates and/or stop dates will be imputed as defined in [Table 27](#) and [Table 28](#) below:

Table 27 Definitions of the Previous or Concomitant Medication Analysis Start Date

Reported Date (from the eCRF)	Analysis Date (Derived)
--/MM/YYYY	01/MM/YYYY
--/--/YYYY	01/01/YYYY
DD/--/----, or --/MM/----, or --/--/----	No imputation

If the imputed start date is after the stop date, then the imputed start date will be one day prior to the stop date.

Table 28 Definitions of the Previous or Concomitant Medication Analysis Stop Date

Reported Date (from the eCRF)	Analysis Date (Derived)
--/MM/YYYY	31/MM/YYYY, or 30/MM/YYYY, or 29/MM/YYYY, or 28/MM/YYYY
--/--/YYYY	31/12/YYYY
DD/--/----, or --/MM/----, or --/--/----	No imputation

AE Onset date

For adverse events, partially missing start dates and/or stop dates will be imputed as defined in [Table 29](#) and [Table 30](#) below:

Table 29 Definitions of the Analysis Adverse Event Onset Date

Reported Date	Date of First Drug Intake	Analysis Date (Derived)
--/MM/YYYY	DD/MM/YYYY	
--/02/2008	14/02/2008	14/02/2008*
--/02/2008	14/02/2007	01/02/2008
--/02/2008	14/02/2009	01/02/2008
--/--/YYYY	DD/MM/YYYY	
--/--/2008	14/02/2008	14/02/2008
--/--/2008	14/02/2007	01/01/2008
--/--/2008	14/02/2009	01/01/2008
DD/--/---- --/MM/---- --/--/----		No imputation

* If the month and year is the same as the month and year of first drug intake, use date of the first drug intake.

Table 30 Definitions of the Analysis Adverse Event End Date

Reported Date	Analysis Date (Derived) *
--/MM/YYYY	31/MM/YYYY or 30/MM/YYYY or 29/MM/YYYY or 28/MM/YYYY
--/--/YYYY	31/12/YYYY
DD/--/----, or --/MM/----, or --/--/----	No imputation

*Death has to be taken into consideration when calculating this.

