5.1.5 Rescue Therapy Guidelines

Rescue therapy guidelines are provided to optimize standardization of the use of rescue therapy by investigators and to ensure safety of the individual study subjects. Use of rescue therapy and reason for rescue therapy should be recorded in the eCRF. If subjects meet the criteria for ESA rescue therapy whilst on dialysis, ESAs will be administered IV or SC according to the Package Insert or SmPC of the respective ESA for dialysis patients.

RBC Transfusion

In the event of acute or severe blood loss, RBC transfusion is allowed if clinically indicated. In a situation where there is no obvious blood loss, RBC transfusion will be permitted if the subject has moderate to severe symptom(s) from his/her anemia, e.g., dyspnea at rest or on mild exertion, and the investigator is of the opinion that the blood transfusion is a medical necessity. Study drug may be continued even if a blood transfusion had been administered.

ESA

If a subject's Hb level has not sufficiently responded to 2 or more dose increases or maximum dose (by body weight) of the study drug and the investigator considers the initiation of an ESA (i.e., EPO analogue) rescue as a medical necessity, the investigator should consider initiating the use of an approved ESA only if all of the following criteria are met:

- The subject's Hb level has not sufficiently responded to 2 or more dose increases in previous 8 weeks or maximum dose (by body weight) of the study drug; **and**
- The subject's Hb is < 8.0 g/dL; **and**
- Reducing the risk of alloimmunization in transplant eligible subjects and/or reduction of other RBC transfusion-related risks is a goal.

The subject may continue on study, however, the subject is not allowed to be administered both ESA and study drug during the same time period. The course of ESA (i.e., the amount that may be administered) will be limited by duration of therapy and effect on Hb, including that 1 course of ESA treatment will not exceed 4 weeks in duration, and that ESA rescue will be stopped as soon as Hb \geq 9 g/dL. Treatment with study drug may be resumed as soon as possible after the following intervals:

- At least 2 days after stop of Epoetin alfa or Epoetin beta, or biosimilar thereof
- At least 1 week after stop of darbepoetin alfa
- At least 2 weeks after stop of methoxy polyethylene glycol-epoetin beta.

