be selected for the calculation of the average LDL cholesterol of weeks 12-28 (see [Table 33](#) and Section [7.11.4](#) for the analysis windows definition and the differentiation between the MMRM and ANCOVA analyses).

For missing LDL imputation rules, refer to Section [7.11.1](#). Baseline LDL is defined as the LDL value on Day 1. If this value is missing, the latest value prior to first study drug administration will be used.

This analysis will also be repeated for fasted values only as a sensitivity analysis.

6.1.2.3 Use and time to first use of rescue therapy (composite of RBC transfusions, ESA use, and IV iron)

RBC transfusion is collected in the Blood Transfusions form of the eCRF. The use of ESAs and IV iron is collected in the Concomitant Medication form of the eCRF (entries where “Given as Anemia Therapy?” is ticked). These medications will be coded into the ATC and WHO-DRL dictionaries.

The following WHO-DRL codes will be classified as ESA: '00909301001', '00928301001', '02198701001', '07973701001', '01703101001'. The following WHO-DRL code where route is INTRAVENOUS will be classified as IV IRON: '00023501001' and '90135401001'. The following WHO-DRL code will be classified as RBC transfusion: '01186901001'.

Only rescue medication that started during the study treatment and up to the end of Efficacy Emergent Period will be taken into account and considered as use of rescue. Medication started at End of Treatment visit will not be considered rescue for patients completed the treatment. Medication Onset Date is the date of the first use of rescue medication.

For a subject with use of rescue therapy, the time to use of rescue therapy will be calculated (in years) as:

$$(\text{First event date} - \text{Analysis date of first dose intake} + 1) / 365.25$$

With ‘First event date’ defined as ‘Date of first dose of rescue medication’ during the Efficacy Emergent Period and ‘Analysis date of first dose intake’ defined in Section [6.5.4](#)

For a subject without use of rescue therapy, the time to censoring is calculated as:

$$[(\text{Date of End of Efficacy Emergent Period} - \text{Analysis date of first dose intake} + 1) / 365.25$$

With date of End of Efficacy Emergent Period defined in Section [7.11.6](#)

6.1.2.4 Change from BL in SF-36 Vitality (VT) Sub-score to the Average VT Sub-score of Weeks 12 to 28

For details on the calculation of the SF-36 VT scale subscore, see Section [6.1.3.14.1](#)

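### SAP 7.11.2 contradicts itself on partial start dates: Table 27 has no first-dose floor, so some on-study rescue and dialysis records can be dated before Day 1 and go uncounted

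*SAP*

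**What the plan says.** SAP 7.11.2 (Missing Dates) opens with a worst-case principle. A partial start date goes to the first possible day, "unless the available information in the partly missing date is equal to the one in the reference date". The section continues: "In this case, the substituted date is set to the reference date". It does not say which date the reference date is.

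Table 29, for adverse event onset, applies that exception with first drug intake as the reference. Its footnote reads: "If the month and year is the same as the month and year of first drug intake, use date of the first drug intake".

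Table 27 covers a wider class of records: "For previous or concomitant medications, including rescue medications and chronic dialysis, partially missing start dates and/or stop dates will be imputed as defined in" Tables 27 and 28. With the day missing, the start becomes 01/MM/YYYY; with day and month missing, 01/01/YYYY. The table has no first-dose column. The only correction beneath it looks at the other end of the record: "If the imputed start date is after the stop date, then the imputed start date will be one day prior to the stop date".

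These dates decide what counts as rescue. SAP 6.1.2.3 says: "Only rescue medication that started during the study treatment and up to the end of Efficacy Emergent Period will be taken into account". SAP 6.1 starts the Efficacy Emergent Period at first dose. The EU primary endpoint (SAP 6.1.1.1) takes its definition of rescue from 6.1.2.3 and makes a subject rescued before response a non-responder.

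**The concern.** A programmer who follows Table 27 and one who follows the general rule can date the same rescue record on opposite sides of Day 1. Under Table 27 as printed, a record dated before Day 1 is not rescue. The consequences are:

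- **EU primary.** A rescued subject who later meets the Hb criteria at two visits within 24 weeks counts as a responder.
- **Test 3, time to first rescue.** If the lost record is the subject's only rescue, the subject is censored instead of having an event.
- **Test 1, Hb in weeks 28-36 without rescue.** SAP 7.11.1 sets Hb to missing for 6 weeks, counted from the start or the end of rescue. A wrong start date either removes that masking or puts it on the wrong dates.
- **Dialysis.** SAP 6.1.2.8 and 7.4.2.8 exclude eGFR from the start of dialysis. The dialysis events in 6.1.3.16 count only in the Safety Emergent Period, which begins at first dose. A start before Day 1 removes all post-baseline eGFR and loses the event.

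The section claims a worst-case principle. For rescue, Table 27 does the opposite, because it removes the event.

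**Working it through.** **1. The conflicting rules on the SAP's own example.** Table 29 uses a first dose of 14/02/2008. SAP 6.1.2.3 gives time = event date − first dose date + 1, then divided by 365.25 for years. The right-hand column applies the Table 29 rule, which is also the general rule if the reference date is first dose.

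| Recorded start | Table 27 | Floor at first dose |
|---|---|---|
| --/02/2008 | 01/02/2008: −13 + 1 = −12 days (−0.033 years), not rescue | 14/02/2008: Day 1, rescue |
| --/--/2008 | 01/01/2008: −44 + 1 = −43 days (−0.118 years), not rescue | 14/02/2008: Day 1, rescue |

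**2. Check against eligibility.** The Table 27 dates lie 13 and 44 days before first dose, which is given on the day of randomization. Protocol 3.2 excludes ESA within 12 weeks (84 days) and transfusion within 8 weeks (56 days) before randomization. For an ESA or a transfusion, both imputed dates would imply a breach of entry criteria. A dialysis start before Day 1 would too, since subjects on dialysis are not eligible.

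**3. Which records are reached.** Assume first-dose dates evenly spread over 2014-2016 and rescue evenly spread over study days. For a month or year of D days, the average number of study days imputed before Day 1 is (D − 1)/2. A first dose on the 1st of the month (or on 1 January) is not hit.

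- Day missing: (30.4 − 1)/2 ≈ 14.7 days. Of Days 1-168, 14.7/168 ≈ 8.8%. Of Days 1-728, 14.7/728 ≈ 2.0%. The latest day hit is Day 30 (first dose on the 2nd of a 31-day month).
- Day and month missing, Days 1-728: (365 − 1)/2 = 182, and 182/728 = 25.0%.
- Day and month missing, Days 1-168: about 1 − 83.5/365 = 77.1%, slightly less for first doses on 1 January. Full enumeration gives 76.9%.
- Days 57-168, after two dose reviews at weeks 4 and 8: enumeration gives 0% with the day missing and 69.2% with day and month missing.

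These shares apply only to records with partial dates.

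**4. Number of subjects.** The documents give no count of partial dates and no placebo rescue rate. Assume 30% of 150 placebo subjects are rescued (45) and 1-5% of records have partial dates. Then 45 × 0.01 = 0.45 and 45 × 0.05 = 2.25 subjects have a partial date. Multiplying by the shares:

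| Rescue spread over | Day missing | Day and month missing |
|---|---|---|
| Days 1-168 | 0.04 to 0.20 | 0.35 to 1.73 |
| Days 1-728 | 0.01 to 0.05 | 0.11 to 0.56 |

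The range 0.45 to 2.25 is therefore an upper bound.

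**5. Effect on the EU primary.** SAP 4 assumes 65% response in 300 roxadustat subjects and 25% in 150 placebo subjects, with at least 95% power. Recomputed power is above 0.999. If 5 placebo subjects were wrongly counted as responders, the placebo rate would be 0.25 + 5/150 = 0.283, and power stays above 0.999.

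**The case against.** **The floor may already apply.** A reader might infer that the plan has no first-dose floor for rescue. The documents do not support that, because the general rule supplies one if the reference date is first dose. What stands is the contradiction: the general rule is hedged, its reference date is undefined, and the specific table for rescue omits it.

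**Table 27 also serves previous medications.** For those, the earliest date is reasonable, and a blanket floor would turn pre-study treatment into on-study rescue. This stands, so the floor must be limited to records known to be on-study.

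**Month-only dates matter little.** Dose adjustments start at week 4 and recur every 4 weeks (Protocol 5.1.2). IV iron rescue requires at least two increases, and ESA rescue requires two increases or maximum dose (Protocol 5.1.5). Within the calendar month of first dose that leaves mainly transfusions. This stands; the exposure is mostly year-only dates. Those should be rare, because concomitant medication is recorded at every visit and data are reviewed before lock.

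**Response does not always flip.** A reader might infer that every lost record reverses the EU outcome. It does so only if the subject later qualifies. ESA rescue starts below 8.0 g/dL and stops at 9 g/dL, whereas response needs at least 11.0 g/dL when baseline exceeds 8.0 g/dL.

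**Direction.** A reader might infer that the fault favours roxadustat. The protocol's amendment rationale expects less rescue on roxadustat, so losses would fall mainly on placebo and shrink the difference.

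**Dialysis has other safeguards.** Quality-of-life questionnaires are scheduled on the first dialysis day, which gives a second date. ESRD-free survival takes ESRD from the adverse event record, where Table 29 applies. The eGFR slope is outside the testing hierarchy.

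**Stop dates.** A reader might infer that Table 28 is wrong too, since a year-only stop runs to 31 December although the protocol says "1 course of ESA treatment will not exceed 4 weeks in duration". The documents do not support calling this an error. The last possible day agrees with the general rule, and PPS criterion 8 (SAP Table 3) anticipates rescue that deviates from the protocol. A cap at the course length could unmask Hb affected by rescue.

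**Conclusion.** The point holds as an internal contradiction in SAP 7.11.2 with a real route to endpoint data. It reaches the EU primary, tests 1 and 3, and the dialysis and eGFR analyses. It does not reach the US primary, which is regardless of rescue, or the EU sensitivity analysis S3 and the Table 17 sensitivity analysis S1, which ignore rescue. The IV iron analysis in 6.1.3.9 is less exposed because it also counts use ongoing at first dose.

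The size is small: at most about 0.5 to 2 placebo subjects under the assumed 30% rescue rate and 1-5% partial dates, and probably fewer. No false-positive risk is shown, and the EU primary conclusion is unlikely to change. The point is still worth correcting, because rescue and responder status in confirmatory tests should not depend on which of two conflicting rules is programmed.

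**What to change.** Make three changes to SAP 7.11.2 before database hard lock:

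1. In Table 27, for rescue and dialysis records known to be on-study (for example from the on-study concomitant medication or transfusion forms), impute the start as the later of the first possible day and the date of first dose.
2. Define the reference date as first dose intake.
3. List every rescue and dialysis record with a partial date for blinded review before lock.

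The listing is needed as well as the floor, for two reasons. Concomitant medication is collected from informed consent, and one IV iron dose before randomization is allowed, so the form alone does not always prove an on-study start. Also, the floor restores the record as rescue but does not recover its true date, so the masking in weeks 28-36 may still need a decision for each record.

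The cost is a few lines of wording and programming, one listing, and no new data. There is one small downside: a year-only rescue given after a genuine response would move to Day 1 and make that subject a non-responder. That is conservative and fits the section's worst-case principle. Leave Table 28 as it is.
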